## **6.5 CONCOMITANT THERAPY**

Any medication or vaccine (including over-the-counter or prescription medicines, vitamins, and/or herbal supplements) that the participant is receiving at the time of enrollment or receives during the study must be recorded along with:

- Reason for use.
- Dates of administration including start and end dates.
- Dosage information including dose and frequency.

The concomitant use of non-sedating antihistamine administration is allowed during the study except for treatment of AD or PN, but dose change of non-sedating antihistamine is not allowed both from Week 11 to Week 12 and from Week 23 to Week 24.

The concomitant use of the following therapies is prohibited during the entire study. Study treatment will need to be discontinued in participants receiving these treatments:

- Systemic immunosuppressive/immunomodulating drugs (eg, systemic corticosteroids, cyclosporine, mycophenolate-mofetil, interferon gamma, Janus kinase inhibitors, azathioprine, methotrexate, hydroxychloroquine, dapsone, sulfasalazine, colchicine, etc).
- Other monoclonal antibodies (which are biological modifiers).
- Phototherapy, including tanning beds.
- Naltrexone or other opioid antagonist.
- Gabapentin, pregabalin, and thalidomide.

The concomitant use of the following therapies is prohibited except if the dose has been stable for at least 3 months prior to screening, but study treatment will not need to be discontinued in participants receiving the treatments listed below. The dose should also remain stable (can be reduced or discontinued if medically indicated), but should not be initiated or increased throughout the study.

- Paroxetine, fluvoxamine, or other SSRIs.
- SNRIs.
- Amitriptyline or other tricyclic or tetracyclic antidepressants.

The concomitant use of the following therapies is also prohibited during the entire study, but study treatment will not need to be discontinued in participants receiving the treatments listed below.

- Intralesional corticosteroid injections and cryotherapy.
- Sedating antihistamine.
- Non-sedating antihistamine used specifically for the treatment of itch secondary to AD or PN.

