**Table 3 - Summary of primary estimand for main endpoints**

Endpoint Category	Estimands			Population-level summary
	Endpoint(s) a	Population	Intercurrent event(s) strategy and missing data handling	
Primary objective: To demonstrate the efficacy of dupilumab on itch response in participants with PN, inadequately controlled on topical prescription therapies or when those therapies are not advisable.				
Primary endpoint	Proportion of participants with improvement (reduction) in worst-itch numeric rating scale (WI-NRS) by $\geq 4$ from baseline to Week 12	ITT	
The intercurrent events will be handled as follows:
 

• Discontinuation of study treatment before Week 12: Off-study treatment data up to Week 12 will be included in the analysis (treatment policy strategy).

• Taking the prohibited medications/procedures and/or rescue medicationsb prior to Week 12: Participants will be considered as non-responders (composite strategy).

 
In addition, the missing data imputation rules are as follows:
 

• Having missing data at Week 12: Participants will be considered as non-responders.

	CMH test adjusted by documented history of atopy (atopic or non-atopic), stable use of TCS/TCI (yes or no), region (countries combined), and baseline antidepressant use (yes or no).

Endpoint Category	Estimands			Population-level summary
	Endpoint(s) a	Population	Intercurrent event(s) strategy and missing data handling	
Secondary objective: To demonstrate the efficacy of dupilumab on additional itch endpoints in participants with PN, inadequately controlled on topical prescription therapies or when those therapies are not advisable.				

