Secondary endpoint	Change from baseline in WI-NRS at Week 24	ITT	
The intercurrent events will be handled as follows:
 
 
Discontinuing the study treatment: all data collected following schedule after treatment discontinuation will be used in the analysis (treatment policy strategy).
 
Taking the prohibited medications/procedures and/or rescue medicationsb prior to Week 24: data will be set to missing values after the medication usage, and the participant's worst postbaseline value on or before the time of the medication usage will be used to impute missing endpoint value (for participants whose postbaseline values are all missing, the participant's baseline will be used to impute the missing endpoint value) (hypothetical strategy)
 
 
In addition, the missing data imputation rules are as follows:
 
 
After discontinuation of the study treatment due to lack of efficacy prior to Week 24: WOCF approach will be used to impute missing data if needed.
 
After discontinuation of the study treatment due to reasons other than lack of efficacy prior to Week 24: multiple imputation (MI) approach will be used to impute missing endpoint value, and this multiple imputation will use all participants excluding participants who have taken the prohibited medications and/or rescue medications prior to Week 24 and excluding participants who discontinue due to lack of efficacy prior to Week 24.
 
	
ANCOVA model with intervention group, documented history of atopy (atopic or non-atopic), stable use of TCS/TCI (yes or no), region (countries combined), baseline antidepressant use (yes or no), and relevant baseline measurement as covariates is used. Statistical inference obtained from all imputed data by ANCOVA model will be combined using Rubin's rule.

a Additional secondary objectives/endpoints are not included in this table but would be handled with a similar strategy as the endpoint type (ie continuous, proportion, time-to-event) at other weeks

b Prohibited medications and/or rescue medications are listed in [Table 5](#).

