## **4.3 PRIMARY ENDPOINT(S) ANALYSIS**

### **4.3.1 Definition of endpoint(s)**

The primary endpoint for this study is the proportion of participants with improvement (reduction) in worst-itch numeric rating scale (WI-NRS) by  $\geq 4$  from baseline to Week 12.

WI-NRS is a patient-reported outcome (PRO) comprised of a single item rated on a scale from 0 (“No itch”) to 10 (“Worst imaginable itch”). Participants are asked to rate the intensity of their worst pruritus (itch) over the past 24 hours using this scale.

The weekly average WI-NRS score at each week, which is defined as the average of daily non-missing scores within the week window of each week (see [Section 5.4](#)), will be used for analyses.

For efficacy analysis, [Table 5](#) presents the prohibited and rescue medications/procedures which will be considered as intercurrent events if the last column indicates as “Yes” and therefore be handled in the estimands for endpoints defined in [Table 3](#).

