Dermatological preparations of high potency or superpotent TCS and TCI	No IMP discontinuation	Yes d (CDG b calcineurin inhibitors and corticosteroids narrow, Ticked 'RESCUE THERAPY' in CRF page)
a.	When yes, the estimand for the intercurrent event handling strategy will be as follows: hypothetical for continuous endpoints, and composite for responder and time-to-event endpoints. When no, a treatment policy strategy will be applied.	
b.	CDG=company drug groupings, CMQ=company MedDRA query, SDG= Standardized drug groupings.	
c.	Only if the antidepressant is initiated during the study or its dose is increased from baseline provided that medication was taken at least 3 months prior to screening.	
d.	As per medical adjudication, see Appendix 7 for details.	
e.	Only if the medication is initiated at Week 12 or Week 24, or the dose is increased from Week 11 to Week 12 or from Week 23 to Week 24.	

Blinded review of prohibited/rescue treatment (medication or procedure) based on [Table 5](#) and a pre-specified algorithm ([Appendix 7](#)) will be implemented before database locks by considering the type of medication or procedure, indication, timing, frequency and the potential impact of the use of the prohibited medications/procedures and rescue medications.

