#### 4.3.2 Main analytical approach

The primary estimand for the primary endpoint is the treatment policy/composite approach as defined in [Table 3](#).

The primary analysis population for the efficacy endpoints will be the ITT population.

The following null hypothesis H0 and alternative hypothesis H1 will be tested for dupilumab against placebo:

- H0: No treatment difference between dupilumab and placebo.
- H1: There is a treatment difference between dupilumab and placebo

The primary analysis will be conducted by using Cochran–Mantel–Haenszel test (CMH) test adjusted by documented history of atopy (atopic or non-atopic), stable use of TCS/TCI (yes or no), region, and baseline anti-depressant use (yes or no). Comparisons of the response rates between dupilumab and placebo will be derived. In addition, odds ratio and response rate difference as well as the corresponding 95% confidence intervals (CI) will be provided along with the p-values.

As defined in [Table 3](#) for participants discontinuing the study treatment before Week 12, their off-study treatment values measured up to Week 12 will be included in the analysis. Participants taking the prohibited medications/procedures and/or rescue medications (see [Table 5](#)) prior to Week 12 or having missing data at Week 12 will be considered non-responders.

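### SAP Table 5 footnote e contradicts the estimand rule it feeds: read literally, prohibited antihistamine use before Week 12 almost never counts for the primary endpoint

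*SAP*

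**What the plan says.** - **SAP 4.3.1** makes Table 5 operative. It lists the medications and procedures "which will be considered as intercurrent events if the last column indicates as" Yes. Table 3 footnote b refers to the same list: "Prohibited medications and/or rescue medications are listed in" Table 5.
- **SAP Table 5** has two prohibited-antihistamine rows: sedating, and non-sedating when used for itch from AD or PN. Both read Yes and carry footnotes d and e.
- **Footnote e** limits that Yes: "Only if the medication is initiated at Week 12 or Week 24, or the dose is increased from Week 11 to Week 12". It adds the matching dose-increase rule for Weeks 23 to 24.
- **Footnote a** applies treatment policy where the answer is No. **Footnote d** refers to medical adjudication under Appendix 7.
- **SAP Table 3**, on taking prohibited or rescue treatment for the primary endpoint: "prior to Week 12: Participants will be considered as non-responders (composite strategy"). **Section 4.3.2** repeats the rule: "prior to Week 12 or having missing data at Week 12 will be considered non-responders".
- **Protocol 6.5 and SAP Appendix 3** prohibit both antihistamine uses for the whole study, without requiring IMP to stop.
- **SAP 4.3.1 and Appendix 7** provide a blinded review that "will be implemented before database locks by considering the type of medication or procedure, indication, timing, frequency and the potential impact" of the use. Appendix 7 item 2 requires adjudication of the remaining listed treatments when given for PN-consistent indications. It weighs the Table 5 criteria together with other factors, including dose, timing and frequency.

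**The concern.** The footnote and the estimand point to different periods. Table 3 looks back over everything before the endpoint week. Footnote e looks only at starts in the endpoint week and at dose increases running into it. A participant who begins a prohibited antihistamine for itch in Week 4 and stays on it is a non-responder under Table 3, but is scored on observed itch under footnote e.

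This choice decides responder status on the primary endpoint. SAP 4.4.1.2 carries the same handling to the Week 24 key secondary endpoints. For continuous endpoints it decides between observed data and worst-observation carry-forward. For time to onset it decides whether later data are used or the participant is censored at Week 24. Adjudication takes place before lock, so the governing rule has to be settled before then.

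**Working it through.** The plan gives no figure to reproduce here. The sample-size response rates are redacted, and the point does not depend on them.

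**1. Inputs.** SAP Table 10 sets Week 11 at Days 75–81 (target 78), Week 12 at Days 82–88 (target 85), Week 23 at Days 159–165 (target 162) and Week 24 at Days 166–172 (target 169). Randomization is Day 1. The SAP does not say how to date a medication start, so using these weeks is an assumption. It is the natural one for the primary endpoint, which is a weekly eDiary average.

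**2. Overlap for the primary endpoint.** I count the days that lie both before Week 12 and inside a footnote e trigger. The period before Week 12 is read as ending before the target day (Days 1–84) or before the window (Days 1–81). Each trigger is read by target day or by window.

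| Period before Week 12 | Start on Day 85 | Start in Days 82–88 | Increase in Days 78–85 | Increase in Days 75–88 |
|---|---|---|---|---|
| Days 1–84 | 0 | 3 (82–84), 3/84 = 3.6% | 7 (78–84), 7/84 = 8.3% | 10 (75–84), 10/84 = 11.9% |
| Days 1–81 | 0 | 0 | 4 (78–81), 4/81 = 4.9% | 7 (75–81), 7/81 = 8.6% |

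Starts on Days 1–81 and increases on Days 1–74 never qualify. Stable use with no start or increase in these windows never qualifies on any day.

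**3. Overlap for Week 24 endpoints**, with the prior period read as Days 1–168:
- Starts: 1 day (Day 85) to 7 (82–88) + 3 (166–168) = 10 days, 10/168 = 6.0%.
- Increases: 8 (78–85) + 7 (162–168) = 15 days to 14 (75–88) + 10 (159–168) = 24 days, 24/168 = 14.3%.

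**4. Two cases, primary endpoint.**
- *Sedating antihistamine for PN itch, started Day 30, dose constant.* Table 3 gives non-response. Footnotes e and a give the observed Week 12 score. Appendix 7 sends the case to adjudication without saying which of the two governs.
- *The same drug started Day 86.* Footnote e is met on the window reading, but the use is not before Week 12 on either reading of that period.

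The two conditions thus miss each other in both directions.

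**5. Where the weeks may come from.** Protocol 6.5 uses them for a different purpose. For non-sedating antihistamines that are permitted because they are not for AD or PN, "dose change of non-sedating antihistamine is not allowed both from Week 11 to Week 12 and from Week 23 to Week 24". By contrast, the antidepressant rows in Table 5 count any start on study: "Only if the antidepressant is initiated during the study or its dose is increased from baseline". This suggests that footnote e was attached to the wrong rows, but the documents do not say so.

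**6. Planned analyses.** SAP 4.3.3 plans no sensitivity analysis for the primary estimand. The as-observed analysis in 4.3.4 keeps all data after prohibited use, so it is more lenient still. The hybrid and tipping-point analyses specify no broader antihistamine definition. None tests the reading in which earlier use counts.

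**7. Unit effect.** With about 75 participants per arm, one reclassified responder moves that arm's rate by 1/75 = 1.33 percentage points. The net effect on the difference is 1.33 × (dupilumab reclassified − placebo reclassified), whose sign is unknown.

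**The case against.** The strongest reply is that the SAP does answer the question. A specific footnote may narrow a general rule, and footnote a supplies treatment policy for what is left out. That stands as a literal reading. A reader might infer that the status of earlier stable use is simply undetermined, and the text does not support that. The defect is that this literal answer conflicts with Table 3 and 4.3.2.

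A second reply is that adjudication decides. The SAP version history says prohibited use counts as non-response after blinded medical confirmation, and timing and impact are listed considerations. This narrows the gap but does not close it, because nothing ranks footnote e against those considerations.

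Third, the narrow rule may be deliberate. Protocol 2.2 describes antihistamines as occasionally used in PN, with efficacy not supported by well-conducted trials. That is plausible, but the SAP gives no such rationale.

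Fourth, the effect may be small. As an illustration only, assume response rates of 10% v 37%, 15% v 44% or 20% v 50%, with 75 per arm and a pooled two-proportion formula. Reclassifying 20% of responders in each arm multiplies the difference by 0.8, a loss of 5.4 to 6.0 points, and power falls from about 98% to 91–93%. Loss of power is therefore not the argument.

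Two further inferences should be resisted. Larger overlaps can be obtained from the Table 11 visit windows (Week 12 as Days 71–126 for IGA PN-S), but the SAP applies neither table to medication dates, and Table 11 does not govern the eDiary endpoint. Nor is there a protocol breach: Protocol Table 6 leaves the selection of these medications to the SAP.

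**Conclusion.** The contradiction is real and stands on the SAP's own text. Footnote e, taken literally, leaves the antihistamine intercurrent event nearly empty for the primary endpoint: 0 to 3 qualifying start days and 4 to 10 qualifying dose-increase days out of 81 to 84. Those counts rest on dating medication by the Table 10 weeks. They are calendar days, not participants and not bias.

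The documents give no antihistamine use data, so the size and direction of any effect on the result are unknown. A reader might infer that the primary result is materially biased, or that the trial cannot proceed without a change; nothing here shows either. It is a should-fix point, because primary and key secondary responder status depends on an unranked choice that no planned analysis tests.

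**What to change.** Before database lock and unblinding, reconcile footnote e with Table 3, Section 4.3.2 and Appendix 7 in one of two ways.

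1. **Remove footnote e from the two prohibited-antihistamine rows**, and word the period so that adjudicated use before or during the endpoint scoring week follows the Table 3 composite rule. Deleting the footnote alone is not enough: a start inside the Week 12 scoring window, which it now names, could drop out because Table 3 covers only use before Week 12.
2. **If footnote e is deliberate, keep it.** Align Table 3 and 4.3.2 with it, define its weeks in days, and state that it binds adjudicators.

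In either case, add one supplementary analysis of the primary and key secondary endpoints using the other reading. Under option 2, that means counting any adjudicated prohibited antihistamine use before the endpoint as non-response.

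The cost is SAP wording and one added analysis. Counting earlier use also means slightly more records to adjudicate and possibly slightly lower response rates. No position is taken on which clinical rule is right; the passages must be reconciled.

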#### 4.3.2 Main analytical approach

The primary estimand for the primary endpoint is the treatment policy/composite approach as defined in [Table 3](#).

The primary analysis population for the efficacy endpoints will be the ITT population.

The following null hypothesis H0 and alternative hypothesis H1 will be tested for dupilumab against placebo:

- H0: No treatment difference between dupilumab and placebo.
- H1: There is a treatment difference between dupilumab and placebo

The primary analysis will be conducted by using Cochran–Mantel–Haenszel test (CMH) test adjusted by documented history of atopy (atopic or non-atopic), stable use of TCS/TCI (yes or no), region, and baseline anti-depressant use (yes or no). Comparisons of the response rates between dupilumab and placebo will be derived. In addition, odds ratio and response rate difference as well as the corresponding 95% confidence intervals (CI) will be provided along with the p-values.

As defined in [Table 3](#) for participants discontinuing the study treatment before Week 12, their off-study treatment values measured up to Week 12 will be included in the analysis. Participants taking the prohibited medications/procedures and/or rescue medications (see [Table 5](#)) prior to Week 12 or having missing data at Week 12 will be considered non-responders.

#### 4.3.3 Sensitivity analysis

For the primary estimand for the primary endpoint, no sensitivity analysis will be performed. However, three supplementary analyses will be performed as described in the section below.

#### 4.3.4 Supplementary analyses

The following supplementary analyses will be performed:

##### As-observed analysis (including all data after taking the prohibited and/or rescue medications)

The data collected after taking all prohibited medications and/or rescue medications will be included in the supplementary analysis to evaluate the robustness of the primary analysis results with respect to the method of handling data while taking the prohibited medications (e.g. treatment policy strategy). In addition, for participants discontinuing the study treatment before Week 12, their off-study treatment values measured up to Week 12 will be included in the analysis. The participants having missing data at Week 12 regardless of reason(s) will be considered non-responders at that timepoint.

##### Hybrid method analysis (the worst-observation carried forward (WOCF) and multiple imputation (MI))

In the primary analysis of change from baseline in WI-NRS (continuous variable) at Week 12, the hybrid method of the WOCF and MI will be used (see [Section 4.4.2](#)). Similar to the continuous variable, the same imputation method will be used in the analysis of the proportion of participants with improvement (reduction) in WI-NRS by  $\geq 4$  from baseline to Week 12, which is consistent for the intercurrent event strategy and missing data handling in the binary variables and continuous variable. That is, after the imputation of continuous WI-NRS data at Week 12 using the hybrid method of the WOCF and MI (see [Section 4.4.2](#)), responders will be defined as participants with improvement in WI-NRS by  $\geq 4$  from baseline to Week 12 in each of the imputed datasets with about 40 imputations, and then the CMH test adjusted by documented history of atopy (atopic or non-atopic), stable use of TCS/TCI (yes or no), region, and baseline anti-depressant use (yes or no) will be used. Statistical inference obtained from all imputed data will be combined using Rubin's rule.

##### Tipping point analysis

The intercurrent events will be handled as follows:

- Discontinuation of study treatment before Week 12: Off-study treatment data up to Week 12 will be included in the analysis (treatment policy strategy).
- Taking the prohibited medications/procedures and/or rescue medications prior to Week 12: Data after the intercurrent events will be censored and then imputed with the below tipping point method

In addition, the missing data imputation rules are as follows:

- Having missing data at Week 12: Data will be imputed with the following tipping point method.

Tipping point method:

- A sequence of analyses will be performed with the adjustment to artificially decrease the response rate in the dupilumab group and increase the response rate in the placebo group with a fixed and definite set of values for data imputation.
- For each combination of increasing response rate in placebo and decreasing response rate in dupilumab, multiple imputed datasets will be generated and analyzed using CMH test. The results obtained from multiple imputed datasets will be combined to generate statistical inference, i.e. p-value and treatment difference between 2 treatment groups.
- A “tipping point” will be identified while the result is no longer statistically significant (i.e. p-value >0.05).

#### 4.3.5 Subgroup analyses

To assess the homogeneity of the treatment effect across various subgroups, analyses will be performed on the primary endpoint across the following subgroups (categories with fewer than 5 participants may be combined with other categories):

- Age group (<65,  $\geq$ 65 years)
- Gender (Male, Female)
- Region
- Territory
- Race (Caucasian/White, Black/of African descent, Asian/Oriental, Others)
- Ethnicity (Hispanic or Latino, Not Hispanic or Latino)
- Baseline weight (<60,  $\geq$ 60- < 90,  $\geq$  90 kg)
- Baseline BMI (<25,  $\geq$ 25- <30,  $\geq$ 30 kg/m^2)
- Participants without a current diagnosis of AD
- History of atopy (atopic or non-atopic)
- Stable use of TCS/TCI (yes or no)
- Antidepressant use (yes or no) at baseline
- Baseline IGA PN-S moderate versus severe (3 vs. 4)
- Participants who have not been impacted by COVID-19 vs impacted by COVID-19 (for participants who have been impacted by the COVID-19, the efficacy data will be descriptive only if the number of participants is not enough to perform statistical tests. Participants impacted by the COVID-19 pandemic are defined as randomized participants with any critical or major deviation related to COVID-19 or who permanently discontinued study intervention or study due to COVID-19.)

To test the interaction between intervention and subgroup factor, a logistic regression model incorporating subgroup-by-treatment interaction will be built for each subgroup factor except the subgroup of participants without a current diagnosis of AD (very few AD participants will be excluded). The model will include all the covariates in the main statistical model plus the subgroup variable and the subgroup-by-treatment interaction. A p-value for the test of interaction will be provided.

In each subgroup, the treatment effects for the primary endpoint will be provided, as well as the corresponding 95% CI, using the same method as applied to the primary analysis. Forest plots will be provided.

